**CONFIDENTIAL**

log-transformed value as the dependent variable and the corresponding log-transformed baseline value as a covariate. Cohorts will be analyzed separately due to different number of doses (1 or 2 in Cohort 1; 2 or 3 in Cohort 2). For Cohort 1, the model will include estimates for treatment effect (formulation/dose combination) within each group, and at the cohort level across groups. The ANCOVA models will include group as a factor for analyses of Cohort 1 with a group by formulation/dose combination interaction term if appropriate. The pre-specified rule for inclusion of the interaction term will be described in the SAP. A factor for country will be included.

Pairwise comparisons of interest will be made in the framework of the ANCOVA model, without adjustments for multiplicity. The primary analyses will be based on the PPS.

Additional secondary and exploratory endpoints will be summarized descriptively, and selected endpoints will be analyzed using ANCOVA for continuous variables or the CMH method [36] stratified by age for dichotomous variables as described previously. Box plots and/or reverse cumulative distribution [RCD] curves will be provided for comparisons of interest.

More specific details about the immunogenicity analyses will be provided in the SAP.

**CCR** . Details regarding exploratory endpoints will be provided in the SAP.

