## 7.0 METHODS OF ANALYSIS AND PRESENTATION

### 7.1 General Considerations

This statistical analysis plan (SAP) is based on protocol Amendment 3, Version 4.0, dated 01 March 2016.

The purpose of this trial is to evaluate the immunogenicity and safety profile of 4 formulations under different dosing regimens in 4 pediatric age ranges. Two cohorts of subjects will be enrolled into the trial (Figure 4.a). Cohort 1 will consist of 4 age groups (4 to <9 years, 1 to <4 years [2 groups] and 6 months to <1 year), enrolled in age-step-down fashion as described in Section 4.4. The youngest age group (Cohort 2, 6 weeks to <6 months) will be the last to complete enrollment. Enrollment into each successive age group is initiated based on DMC recommendation. Hereafter the age groups (5 groups covering 4 age ranges) will be designated as 'group'. The factors under investigation for each group within each cohort include: formulation (4 formulation arms within each group); and number of doses (2 levels for each formulation within each group). For groups 1, 2, 2a, and 3 (in Cohort 1), the number of active doses will be 1 or 2 doses. For group 4 (Cohort 2), the number of active doses will be 2 or 3. Within each cohort, subjects are randomized to 1 of 8 trial arms (2 dose levels for 4 formulations), with group as a stratification factor. The purpose of Group 2a is to evaluate the safety and selected immunogenicity endpoints in subjects in the same age range as Group 2, but who receive the recently manufactured NoV bivalent VLP vaccine. Statistical methods described in the following sections will be essentially the same, but will be done only for the endpoints indicated in Section 5.2.

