Immunogenicity and safety endpoints will be summarized descriptively (frequency and percent for categorical data; and number of subjects with non-missing observations, mean [or geometric mean], standard deviation [SD] [or geometric standard deviation {GSD}], median, minimum, and maximum for continuous data, unless specified otherwise) at all relevant study visits, as appropriate. In summary tables for categorical data for which categories are defined on the electronic case report form (eCRF), all categories will be presented as specified, even if the subject count within that category is zero. For other categorical data (eg, AEs and medications), only categories with at least 1 subject will be presented. Unless otherwise specified, for each group summarized, category percentages will be based on the number of subjects in the group with non-missing data and the non-missing 'n' will be displayed for each count/percentage.

Minimum and maximum values will be presented using the same number of decimal places as the recorded data. Means, geometric means, least squares means (LS Means), and medians will be presented to 1 more decimal place than the recorded data. SD and GSD will be presented to 2 more decimal places than the recorded data. The confidence interval (CI) about a parameter estimate will be presented using the same number of decimal places as the parameter estimate (ie, 1 more decimal place than the recorded data). Percentages will be presented to 1 decimal place (eg, 80.3%). All p-values will be rounded to 3 decimal places. If a p-value is less than 0.001, it will be reported as “<0.001”; if a p-value is greater than 0.999, it will be reported as “>0.999”.

In general, summaries and analyses will be provided by formulation/dose combination (the 8 available combinations of the 4 formulations and 2 dose groups), by age group and by cohort. For the by-cohort summaries and analyses, those for Cohort 1 are pooled over the 3 age groups (ie, groups 1 – 3).

Unless otherwise specified, all data collected during the trial will be presented in the subject listings. For all listings where information on screen failure is collected, the screen failures data will be presented at the end of the listing.

All statistical analyses will be generated using SAS Version 9.2 or higher.

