## **7.8 Immunogenicity Analysis**

### *General Methodology*

The primary population for immunogenicity analyses will be the PPS. Supportive immunogenicity analyses on primary and key secondary endpoints will also be performed using FAS.

Descriptive statistics for the primary, secondary, and exploratory endpoints will be computed for all available assays at all relevant time points and include the following:

- Titer values (eg, GMT, BT50, GMFR): geometric mean, GSD, 95% CIs, minimum, and maximum;
- Other continuous endpoints: mean, SD, median, minimum, and maximum;
- Categorical variable (eg, seroresponse rate): number and percentage of subjects, and 95% CIs in specified categories. The 95% CI of seroresponse rate will be calculated using exact (Clopper-Pearson) method.

Cohorts will be analyzed separately due to different number of doses (1 or 2 in Cohort 1; 2 or 3 in Cohort 2).

Analysis of covariance (ANCOVA) will be conducted for continuous outcome parameters (eg, GMT, GMFR), examining the effect of formulation/dose combination using log-transformed values of the endpoint as the dependent variable and the corresponding log-transformed baseline (pre-vaccination) value as a continuous covariate. The ANCOVA models will include group as a factor for analyses of Cohort 1 with a group by formulation/dose combination interaction term if

appropriate as follows. If the interaction term p-value is  $\leq 0.05$ , the term will remain in the model. If the p-value is  $>0.05$  it will be removed. For Cohort 1, the model will include estimates for treatment (formulation/dose combination) effect within each group, and at the cohort level across groups. A factor for country will be included in all models.

For binomial outcomes the Cochran-Mantel-Haenszel (CMH) method [2] for difference in proportions will be conducted, stratified by group (Cohort 1).

All pairwise comparisons (with the lower level as a reference group) will be presented, without adjustments for multiplicity.

Pre-specified comparisons of interest will be tested. The pre-specified comparisons of interest are the following:

- “A: 15/15, 1 Dose” vs. “A: 15/15, 2 Dose”
- “A: 15/15, 1 Dose” vs. “B: 15/50, 2 Dose”
- “B: 15/50, 1 Dose” vs. “C: 50/50, 1 Dose”
- “B: 15/50, 1 Dose” vs. “B: 15/50, 2 Dose”
- “C: 50/50, 1 Dose” vs. “B: 15/50, 2 Dose”
- “C: 50/50, 1 Dose” vs. “C: 50/50, 2 Dose”
- “C: 50/50, 1 Dose” vs. “D: 50/150, 2 Dose”
- “D: 50/150, 1 Dose” vs. “D: 50/150, 2 Dose”

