#### Secondary and Exploratory Continuous Immunogenicity Endpoints

The secondary and exploratory continuous immunogenicity endpoints are listed below:

- CCI
- 
- 
- 
- 
- 
- 
- 

GMT, BT50 and GMFR will be summarized descriptively, as described in the General Methodology of Section 7.9, for each of the 8 formulation/dose combinations (4 formulation arms; 1 and 2 [or 2 and 3] doses), by group, at each scheduled time point. These summaries will

also be provided at the cohort level, ie, by pooling subjects across the relevant groups. These summaries will be provided for the subjects in the PPS and FAS.

The GMT and BT50 will be calculated as the anti-logarithm of  $\sum(\log \text{transformed titer}/n)$ , ie, as the anti-logarithm transformation of the mean of the log-transformed titer, where n is the number of subjects with titer information. The GSD for GMT and BT50 will be calculated as the anti-logarithm transformation of the standard deviation of the log-transformed titer. The 95% CI will be calculated as the anti-logarithm transformation of the upper and lower limits for a two-sided CI for the mean of the log-transformed titers.

[figure not shown]
GMFR will be calculated as anti-logarithm of  $\sum (\log \text{transformed (post-vaccination titer/ pre-vaccination titer)}/n)$ . The GSD and 95% CIs for GMFR will be calculated similarly to those for GMT and BT50.

GMT, BT50 and GMFR will be analyzed with an ANCOVA model examining the effect of formulation/dose combination using the log-transformed value as the dependent variable and the corresponding log-transformed baseline value as a covariate. The ANCOVA models will include group as a factor for analyses of Cohort 1 with a group by formulation/dose combination interaction term included if appropriate, as follows. If the interaction term p-value is  $\leq 0.05$ , the term will remain in the model. If the p-value is  $>0.05$  it will be removed. For Cohort 1, the model will include estimates for treatment (formulation/dose combination) effect within each group, and at the cohort level across groups. A factor for country will be included. All the applicable pairwise comparisons will be provided with lower levels as the reference groups, with no adjustments for multiplicity. The 14 comparisons of interest listed in the *General Methodology* of Section 7.8 will be tested. The analyses will be based on the PPS.

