## **7.12 Interim Analysis**

Interim analyses are planned in this study: Day 57 for Cohort 1 and Day 140 for Cohort 2 (primary analysis time point). The Day 57 interim for Cohort 1 will be provided initially for Groups 1 and 2, which will complete Day 57 substantially earlier than Groups 2a and 3. The Day 57 IA for Groups 2a and 3 combined will be provided at a later time. Thus, the Day 57 IA will be conducted in two parts to be followed by the Day 140 IA in Group 4. Interim analyses will be finalized after the primary safety and immunogenicity data for the group are available, ie, after all subjects from Cohort 1 have completed Day 57 or terminated early and after all subjects from Cohort 2 have completed Day 140 or terminated early.

The interim analyses will be performed by a separate group of unblinded statisticians and programmers at Quintiles who will have access to individual treatment assignments, but will not be involved in subsequent study conduct. The rest of the personnel involved in the conduct of the study, including those at Takeda, Quintiles, and the study sites, will remain blinded to the

individual subject data (including treatment assignments) until unblinding after database lock (Day 210 for Cohort 1 and Day 293 for Cohort 2).

The interim results will be shared with limited personnel at Takeda and will include only aggregate group unblinded reports. Individual results will not be shared with any Takeda personnel or the Quintiles blinded team. The list of team members from the study who are given access to the group results will be documented in an unblinding plan. Statistical Methodology for interim analyses will be the same as for final study analysis, described in previous sections, but may be a subset of the analyses to be performed at the end of the study.

Data listings containing subject-level unblinding information will not be generated for either the Day 57 or Day 140 analyses for Cohort 1 and Cohort 2, respectively.

Complete clinical database subject listings will be provided only at final analysis (ie, Day 210 for Cohort 1 and Day 393 for Cohort 2) after the database is locked

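### SAP 7.8 drops the group-by-treatment interaction at p>0.05 yet takes within-group effects from that model, so all Cohort 1 groups then get the same contrast

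*SAP*

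**What the plan says.** SAP 7.8 (General Methodology) specifies one ANCOVA for the continuous immunogenicity endpoints in Cohort 1. The dependent variable is the log endpoint. The model contains formulation/dose combination (8 levels), group, country and the "log-transformed baseline (pre-vaccination) value as a continuous covariate". A group by formulation/dose interaction is tested. If p is 0.05 or less, "the term will remain in the model"; otherwise it is taken out. The following sentence carries no condition: "For Cohort 1, the model will include estimates for treatment (formulation/dose combination) effect within each group, and at the cohort level across groups".

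SAP 7.8.2 repeats both the rule and that sentence for GMT, BT50 and GMFR. Protocol 13.1.3 has the same within-group requirement and hands the rule over: "The pre-specified rule for inclusion of the interaction term will be described in the SAP".

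Three other passages bear on this:

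- SAP 7.1, on why the extra group was added: "The purpose of Group 2a is to evaluate the safety and selected immunogenicity endpoints in subjects in the same age range as Group 2", but with the recently manufactured vaccine.
- SAP 7.12, on the interims (Groups 1 and 2 first, Groups 2a and 3 later): "Statistical Methodology for interim analyses will be the same as for final study analysis".
- SAP 7.1, on by-cohort results: "those for Cohort 1 are pooled over the 3 age groups". The SAP's change rationale in 7.13 instead treats Cohort 1 as four groups, with group and not age range as the model factor.

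**The concern.** The rule and the required output conflict. A model without the interaction cannot produce group-specific treatment effects. Any contrast read from it for a given group is the cohort-level contrast under another label, with a CI that reflects the pooled sample.

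This matters because group carries both age and manufacturing source. Groups 1 and 2 received the original material; Groups 2a and 3 receive the recently manufactured one. When the term is dropped in the full Cohort 1 fit, Groups 2 and 2a show identical dose and formulation contrasts by construction. A reader could take that agreement as evidence that the two materials, or the age ranges, behave alike. The per-group descriptive CIs might then point elsewhere for the same group, and the SAP does not say which result governs. Because the rule runs separately for each endpoint, some assays could show group-specific contrasts while others show repeated pooled ones.

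**Working it through.** **Plan's own figures.** The documents give no power, SD or expected heterogeneity for this ANCOVA; the trial is declared descriptive (Protocol 13.3, SAP 6.0). The one calculable design figure, Protocol Table 13-a, reproduces: 1 − (1 − 0.0033)^480 = 79.5%. It confirms N = 480 for Cohort 1 but does not bear on this point.

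**Inputs.** From SAP 4.4: four groups, eight formulation/dose combinations, about 15 children per combination per group (4 × 8 × 15 = 480). From SAP 7.8: the model and the 0.05 threshold. Assumed: log10 residual SD (after baseline and country) of 0.4, 0.5 or 0.6, and a true 2-fold second-dose gain where stated, which is log10 2 = 0.301, or 0.75, 0.60 or 0.50 SD.

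**Step 1: algebra.** Without the interaction, for group g and arm j,

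E[log Y] = γ_g + τ_j + country + β × log baseline.

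The contrast of arms j and k in group g is τ_j − τ_k. The group term cancels, so estimate, standard error and CI are the same in every group, whatever the data.

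**Step 2: numerical confirmation.** Both models were fitted to one simulated data set (residual SD 1), comparing formulation A with 2 doses against 1 dose:

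| Model | Group 1 | Group 2 | Group 2a | Group 3 | CI half-width |
|---|---|---|---|---|---|
| Without interaction | 0.439 | 0.439 | 0.439 | 0.439 | 0.38 |
| With interaction | 0.149 | 0.191 | 1.185 | 0.230 | 0.75 |

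The interaction p-value in this data set was 0.005, so the rule would have kept the term; the table illustrates the algebra only. Log fold rise as the outcome gives the same contrasts as log titer.

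**Step 3: width.** The half-width is 1.96 × √(2/n) × SD.

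- n = 15 per arm: 0.716 SD.
- n = 60 per arm: 0.358 SD, a ratio of √(15/60) = 0.50.
- Two-group interim, n = 30 per arm: a ratio of √(15/30) = 0.71.

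At SD 0.5, the multiplicative margin on the ratio is 10^0.358 = 2.28 with 15 per arm and 10^0.179 = 1.51 with 60.

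**Step 4: how often the term is dropped.** With four groups the test has 3 × 7 = 21 df. If the second-dose effect in one group differs from the other three by δ SD in all formulations, the noncentrality is 15 × 1.5 × δ² = 22.5δ². Power at the 0.05 level is 8, 21, 49 and 81% for δ = 0.25, 0.5, 0.75 and 1.0.

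**Step 5: the rule as a whole.** Each simulated trial (40,000 per scenario) tests the interaction, selects the model, and takes the A 2-dose versus A 1-dose contrast in a group that departs from the others. Results are for SD 0.4/0.5/0.6.

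| Scenario | Term kept, % | Coverage of nominal 95% CI, % |
|---|---|---|
| (a) One of four groups gains, all formulations | 49/30/21 | 53/50/56 |
| (b) One of four groups gains, formulation A only | 20/14/10 | 29/39/51 |
| (c) Groups 2a and 3 gain, Groups 1 and 2 do not | 65/41/28 | 78/75/78 |
| As (a), three groups in the model | not tabulated | 65/66/71 |
| As (a), two groups in the model | 52/33/23 | 83/84/86 |
| One of four groups deviates by 0.25 SD | not tabulated | 83 |
| Equal effects in all groups | not tabulated | 95 |

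The back-transformed mean ratio reported for the gaining group is 1.60/1.45/1.37 in (a) and 1.37/1.32/1.29 in (b), against a true 2.0. The direction follows from Step 1: without the interaction, the expected contrast in (a) is one quarter of the log gain, 2^(1/4) = 1.19. In (a), coverage in a group that does not gain is 88/89/90%. Always keeping the interaction gives about 95% throughout.

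**The case against.** The strongest case against runs as follows.

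- **Another source may exist.** SAP 7.1 says that, in general, summaries and analyses are given by group as well as by cohort, which could support per-group ANCOVAs. But it is a general presentation statement and names no such model. It does not override the specific instruction in 7.8 that the Cohort 1 model supplies the within-group estimates.
- **Groups 2 and 2a are in separate interim models.** At Day 57, Groups 1 and 2 are analysed before Groups 2a and 3, so Groups 2 and 2a are not forced to agree there. This stands, and the two-group losses are smaller. They share a model only in a full Cohort 1 fit, and whether that fit has three or four groups needs settling, because 7.1 and 7.13 differ.
- **The group main effect stays in the model.** Correct: adjusted mean levels can still differ between Groups 2 and 2a. Only differences in arm contrasts are suppressed.
- **Stakes are limited.** Also correct. The trial is descriptive, the rule touches secondary and exploratory continuous endpoints, and no decision rule uses these contrasts. Per-group GMT, BT50 and GMFR with CIs are planned, but they are not baseline- and country-adjusted treatment contrasts.
- **Pooling can reduce error.** At 15 per cell, with one deviating group, the rule has lower root mean square error (RMSE) than always keeping the term for deviations up to about 0.4 SD: 0.28 against 0.36 SD at a deviation of 0.25, and 0.36 against 0.37 at 0.4. In (c) it is 0.34 against 0.37 at SD 0.6 and 0.37 against 0.36 at SD 0.5. In (a) at SD 0.5 the rule is worse, 0.47 against 0.37. This is a fair argument for a pooled estimate presented as pooled. It does not justify a 95% CI labelled as group-specific that does not have that coverage.

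**Conclusion.** The concern holds: the rule is wrong as written and should be fixed. That the contrasts and CIs become identical when the term is dropped is algebra and needs no assumption. The size of the harm does depend on assumptions the documents cannot settle (residual SD, pattern and size of heterogeneity, number of groups in the model). Over the range examined, coverage for a deviating group runs from 29% when one group differs in one formulation, through about 50% when one group differs in all, to 83–86% with two groups, and it is 95% when effects are equal. The cohort-level ANCOVA contrasts, the primary CMH seroresponse analysis and the per-group descriptive summaries of GMT, BT50, GMFR and seroresponse are outside this point.

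**What to change.** Delete the p-value rule in SAP 7.8 and 7.8.2 and replace it with:

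> Within-group contrasts will always be estimated from the ANCOVA that includes the group by formulation/dose combination interaction. Cohort-level contrasts will be estimated from the ANCOVA without it. The interaction p-value will be reported for description only and will not determine which model is used.

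Separate ANCOVAs within each group would also be an acceptable source for the within-group contrasts. The same edit should state whether Group 2a belongs to the pooled Cohort 1 model, so that 7.1 and 7.13 agree.

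The cost is wording in two SAP sections plus that clarification. Protocol 13.1.3 leaves the rule to the SAP and need not change, and no new data are required. The statistical price is wider within-group intervals: at SD 0.5, a factor of 2.28 either side of the ratio instead of 1.51. If effects really are equal across groups, within-group RMSE rises from 0.21 to 0.37 SD. The cohort-level contrasts keep the pooled precision.
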